10.0 ADVERSE EVENTS

10.1 Definitions

10.1.1 Pretreatment Event Definition

A pretreatment event is any untoward medical occurrence in a patient or subject who has signed informed consent to participate in a study but before administration of any study medication; it does not necessarily have to have a causal relationship with study participation.

10.1.2 AE Definition

AE means any untoward medical occurrence in a patient or subject administered a pharmaceutical product; the untoward medical occurrence does not necessarily have a causal relationship with this treatment. An AE can therefore be any unfavorable and unintended sign (including an abnormal

laboratory finding), symptom, or disease temporally associated with the use of a medicinal (investigational) product whether or not it is related to the medicinal product. This includes any newly occurring event or a previous condition that has increased in severity or frequency since the administration of study drug.

An abnormal laboratory value will not be assessed as an AE unless that value leads to discontinuation or delay in treatment, dose modification, therapeutic intervention, or is considered by the investigator to be a clinically significant change from baseline.

10.1.3 SAE Definition

SAE means any untoward medical occurrence that at any dose:

- Results in death.
- Is life-threatening (refers to an AE in which the patient was at risk of death at the time of the event. It does not refer to an event which hypothetically might have caused death if it were more severe).
- Requires inpatient hospitalization or prolongation of an existing hospitalization (see [clarification](#) in the paragraph in Section 10.2 on planned hospitalizations).
- Results in persistent or significant disability or incapacity. (Disability is defined as a substantial disruption of a person's ability to conduct normal life functions).
- Is a congenital anomaly/birth defect.
- Is a medically important event. This refers to an AE that may not result in death, be immediately life-threatening, or require hospitalization, but may be considered serious when, on the basis of appropriate medical judgment, it may jeopardize the patient, require medical or surgical intervention to prevent one of the outcomes listed above, or involves suspected transmission via a medicinal product of an infectious agent. Examples of such medical events include allergic bronchospasm requiring intensive treatment in an emergency room or at home, blood dyscrasias or convulsions that do not result in inpatient hospitalization, or the development of drug dependency or drug abuse; any organism, virus, or infectious particle (eg, prion protein transmitting transmissible spongiform encephalopathy), pathogenic or nonpathogenic, is considered an infectious agent.

In this study, intensity for each AE, including any lab abnormality, will be determined using the NCI CTCAE, Version 5.0, effective 01 April 2018. The signs and symptoms of disease progression should be reported as AEs in the appropriate section of the eCRF, however should not be reported by the Preferred Term (PT) of disease progression. Disease progression assessed by measurement of malignant lesions on radiographs or other methods should not be reported as an AE.

Clarification should be made between an SAE and an AE that is considered severe in intensity (Grade 3 or 4) because the terms *serious* and *severe* are NOT synonymous. The general term *severe* is often used to describe the intensity (severity) of a specific event; the event itself, however,

may be of relatively minor medical significance (such as a Grade 3 headache). This is NOT the same as *serious*, which is based on patient/event outcome or action criteria described above and is usually associated with events that pose a threat to a patient's life or ability to function. A severe AE (Grade 3 or 4) does not necessarily need to be considered serious. For example, a white blood cell count of 1000/mm³ to less than 2000/mm³ is considered Grade 3 (severe) but may not be considered serious. Seriousness (not intensity) serves as a guide for defining regulatory reporting obligations.

10.1.4 Adverse Events of Special Interest (AESI)

An AESI (serious or nonserious) is an AE of scientific and medical concern specific to the product or program, for which ongoing monitoring and rapid communication by the investigator to Takeda sponsor may be appropriate. Such events may require further investigation in order to characterize and understand them. Serious AESIs will be reported to Takeda Global Pharmacovigilance in an expedited manner irrespective of the event's seriousness or causal relationship. Instruction regarding how and when AESIs should be reported to Takeda are provided in Section 10.2.1.

10.2 Procedures for Recording and Reporting AEs and SAEs

All AEs spontaneously reported by the patient and/or in response to an open question from study personnel or revealed by observation, physical examination, or other diagnostic procedures will be recorded on the appropriate page of the eCRF (see Section 10.3 for the period of observation). Any clinically relevant deterioration in laboratory assessments or other clinical finding is considered an AE. When possible, signs and symptoms indicating a common underlying pathology should be noted as single comprehensive event.

Regardless of causality, SAEs must be reported by the investigator to the Takeda Global Pharmacovigilance department or designee within 24 hours of becoming aware of the event. This will be done by transmitting an electronic data capture (EDC) SAE report, the preferred method of reporting SAEs. If access to EDC is not feasible within 24 hours of receiving the event, the paper SAE forms should be submitted via fax (see fax numbers below). If a fax is used for transmission, site personnel must make every effort to confirm successful transmission of all pages and include an e-mail address on the fax cover sheet so that an acknowledgment of receipt can be returned via e-mail within 1 business day.

E-mail submission of scanned SAE forms should only be used in the event fax transmission is not possible and EDC transmission is not feasible within 24 hours of receiving the event. If e-mail is used, site personnel must make every effort to confirm successful transmission by awaiting acknowledgment of receipt via e-mail within 1 business day.

If SAEs are reported via fax or by e-mail, the EDC system must be updated as soon as possible with the appropriate information. A sample of the paper-based SAE form and processing directions are in the Study Manual. Information in the SAE report or form must be consistent with the data provided on the eCRF.

If information not available at the time of the first report becomes available at a later date, the investigator will transmit a follow-up EDC SAE report (or a paper-based SAE form if an EDC

SAE report is not feasible) or provide other documentation immediately within 24 hours of receipt. Copies of any relevant data from the hospital notes (eg, ECGs, laboratory tests, discharge summary, postmortem results) should be sent to the addressee, if requested.

Fax Numbers

United States and Canada
[contact]

Rest of world
[contact]

E-Mail Address

[contact]

All SAEs should be followed up until resolution or permanent outcome of the event. The timelines and procedure for follow-up reports are the same as those for the initial report.

Planned hospital admissions or surgical procedures for an illness or disease that existed *before study drug was given* are not to be considered AEs unless the condition deteriorated in an unexpected manner during the trial (eg, surgery was performed earlier or later than planned).

For both serious and nonserious AEs, the investigator must determine both the severity (toxicity grade) of the event and the relationship of the event to study drug administration.

Severity (toxicity grade) for each AE, including any lab abnormality, will be determined using the NCI CTCAE, Version 5.0, effective date 01 April 2018. The criteria are provided in the Study Manual.

Relationship of the event to study drug administration (ie, its causality) will be determined by the investigator responding yes (related) or no (unrelated) to this question: “Is there a reasonable possibility that the AE is associated with the study drug?”

10.2.1 AESI Reporting

10.2.1.1 Modakafusp Alfa

An IRR is a type of hypersensitivity reaction that develops during or shortly after administration of a drug. Signs and symptoms may include pruritus, urticaria, fever, rigors/chills, diaphoresis, bronchospasms, and cardiovascular collapse. Specific management instruction is included in Section 8.10.1. In modakafusp alfa studies, IRRs are designated as AESIs. When reporting IRRs in the eCRF, the signs and symptoms should be recorded and should be marked as an AESI.

10.2.1.2 Pembrolizumab

The following AEs are considered AESIs:

- Pneumonitis.
- Hepatitis.

- Colitis.
- Nephritis.
- Dermatologic reactions.
- Myocarditis.
- IRR.
- Endocrinopathies, including thyroid disorders, adrenal insufficiency, type 1 diabetes mellitus, and hypophysitis.

Serious AESIs will be reported to Takeda Global Pharmacovigilance in an expedited manner irrespective of the event's causal relationship. Further, patients will be advised to promptly report signs and symptoms that may indicate IRRs, including fever, chills, dizziness, nausea, vomiting, flushing, cough, headache, and rash during or soon after end of infusion.

10.3 Monitoring of AEs and Period of Observation

AEs, both nonserious and serious, will be monitored throughout the study as follows:

- AEs will be reported from the signing of informed consent through 30 days after administration of the last dose of study drug or the start of subsequent anticancer therapy, whichever occurs first, and recorded in the eCRFs. The reporting period for irAEs (Section 8.6.3.2) is extended to 90 days after administration of the last dose of study drug or the start of subsequent anticancer therapy, whichever occurs first, and recorded in the eCRFs.
- SAEs will be reported to the Takeda Global Pharmacovigilance department or designee from the signing of informed consent through 30 days after administration of the last dose of study drug, even if the patient starts nonprotocol therapy, and recorded in the eCRF. The reporting period for serious irAEs is extended to 90 days after administration of the last dose of study drug. After this period, only related SAEs must be reported to the Takeda Global Pharmacovigilance department or designee. SAEs should be monitored until they are resolved or are clearly determined to be caused by a patient's stable or chronic condition or intercurrent illness(es).

10.4 Procedures for Reporting Drug Exposure During Pregnancy and Birth Events

Any participant who is found to be pregnant during the study should be withdrawn and modakafusp alfa, and pembrolizumab if applicable, immediately discontinued. In addition, any pregnancies in the partner of a study participant during the study should also be recorded, after authorization from the study participant's partner.

If a participant or a study participant's partner agrees to their primary care physician being informed, the investigator should notify the primary care physician that the participant was participating in a clinical study at the time of the pregnancy and provide details of the study drug the subject received.

All pregnancies, including those in partners of study participants, will be followed to final outcome using the pregnancy form. The outcome, including any premature termination, must be reported to the sponsor. An evaluation after the birth of the child will also be conducted.

10.5 Procedures for Reporting Product Complaints or Medication Errors (Including Overdose)

A product complaint is a verbal, written, or electronic expression that implies dissatisfaction regarding the identity, strength, purity, quality, or stability of a drug product. Individuals who identify a potential product complaint situation should immediately report this via the phone numbers or e-mail addresses provided in the Study Manual.

A medication error is a preventable event that involves an identifiable patient and that leads to inappropriate medication use, which may result in patient harm. Whereas overdoses and underdoses constitute medication errors, doses missed inadvertently by a patient do not. Individuals who identify a potential medication error (including overdose) situation should immediately report this via the phone numbers or e-mail addresses provided in the Study Manual.

Product complaints in and of themselves are not AEs. If a product complaint or a medication error results in an SAE, the SAE should be reported.

10.6 Safety Reporting to Investigators, IRBs or IECs, and Regulatory Authorities

The sponsor will be responsible for reporting all suspected unexpected serious adverse reactions (SUSARs) and any other applicable SAEs to regulatory authorities, investigators, and IRBs or IECs as applicable, in accordance with national regulations in the countries where the study is conducted. Relative to the first awareness of the event by/or further provision to the sponsor or sponsor's designee, SUSARs will be submitted to the regulatory authorities as an expedited report within 7 days for fatal and life-threatening events and 15 days for other serious events, unless otherwise required by national regulations. The sponsor will also prepare an expedited report for other safety issues where these might materially alter the current benefit-risk assessment of an investigational medicinal product or that would be sufficient to consider changes in the investigational medicinal product's administration or in the overall conduct of the trial. The investigational site also will forward a copy of all expedited reports to his or her IRB or IEC in accordance with national regulations.

11.0 STUDY-SPECIFIC COMMITTEES

No steering committee, external data safety monitoring committee, or clinical endpoint committee will be used in this study.

12.0 DATA HANDLING AND RECORDKEEPING

The full details of procedures for data handling will be documented in the data management plan. If selected for coding, AEs, medical history, and concurrent conditions will be coded using the Medical Dictionary for Regulatory Activities (MedDRA). Drugs will be coded using the World Health Organization Drug Dictionary.

12.1 eCRFs

Completed eCRFs are required for each subject who signs an ICF.

The sponsor or its designee will supply investigative sites with access to eCRFs and will arrange to train appropriate site staff in the use of the eCRF. These forms are used to transmit the information collected in the performance of this study to the sponsor, CRO partners, and regulatory authorities. Investigative sites must complete eCRFs in English.

After completion of the entry process, computer logic checks will be run to identify items, such as inconsistent dates, missing data, and questionable values. Queries may be issued by Takeda personnel (or designees) and will be answered by the site.

Any change of, modification of, or addition to the data on the eCRFs should be made by the investigator or appropriate site personnel. Corrections to eCRFs are recorded in an audit trail that captures the old information, the new information, identification of the person making the correction, the date the correction was made, and the reason for change.

The principal investigator must review the eCRFs for completeness and accuracy and must sign and date the appropriate eCRFs as indicated. Furthermore, the principal investigator must retain full responsibility for the accuracy and authenticity of all data entered on the eCRFs.

eCRFs will be reviewed for completeness and acceptability at the study site during periodic visits by study monitors. The sponsor or its designee will be permitted to review the subject's medical and hospital records pertinent to the study to ensure accuracy of the eCRFs. The completed eCRFs are the sole property of the sponsor and should not be made available in any form to third parties, except for authorized representatives of appropriate governmental health or regulatory authorities, without written permission of the sponsor.

12.2 Record Retention

The investigator agrees to keep the records stipulated in Section 12.1 and those documents that include (but are not limited to) the study-specific documents, the identification log of all participating patients, medical records, temporary media such as thermal sensitive paper, source worksheets, all original signed and dated ICFs, subject authorization forms regarding the use of personal health information (if separate from the ICFs), electronic copy of eCRFs, including the audit trail, and detailed records of drug disposition to enable evaluations or audits from regulatory authorities, the sponsor or its designees. Any source documentation printed on degradable thermal sensitive paper should be photocopied by the site and filed with the original in the subject's chart to ensure long term legibility. Furthermore, ICH E6 Section 4.9.5 requires the investigator to retain essential documents specified in ICH E6 (Section 8) until at least 2 years after the last approval of a marketing application for a specified drug indication being investigated or, if an application is not approved, until at least 2 years after the investigation is discontinued and regulatory authorities are notified. In addition, ICH E6 Section 4.9.5 states that the study records should be retained until an amount of time specified by applicable regulatory requirements or for a time specified in the Clinical Study Site Agreement between the investigator and sponsor.

Refer to the Clinical Study Site Agreement for the sponsor's requirements on record retention. The investigator should contact and receive written approval from the sponsor before disposing of any such documents.

13.0 STATISTICAL METHODS

A statistical analysis plan will be prepared and finalized before database lock. This document will provide further details regarding the definition of analysis variables and analysis methodology to address all study objectives.

13.1 Determination of Sample Size

13.1.1 Phase 1b Dose Escalation

It is expected that approximately 30 patients will be enrolled in Phase 1b. A minimum of 3 patients will be enrolled in the starting dose level. Starting from the second dose level, an adaptive BLRM guided by the EWOC principle will be used for all subsequent dose escalation recommendations. The details of the dose escalation are specified in Section 8.3 and the description and operating characteristics of the BLRM for dose escalation are included in [Appendix E](#).

13.1.2 Phase 2 Dose Expansion

The study will enroll up to 25 patients in each phase 2 dose expansion disease subgroup. A Bayesian predictive probability design was used to allow multiple futility analyses to stop early for futility. Enrollment into phase 2 will be initiated once the RP2D of modakafusp alfa has been determined in phase 1b of the study.

The combination treatment cohorts will begin with a single safety-lead in period during which 3 to 9 patients will be evaluated for safety and tolerability during their first cycle of modakafusp alfa with pembrolizumab.

Up to 25 patients will be enrolled in each of the 3 disease subgroup cohorts. Assuming 3 to 9 safety lead-in patients, the total sample size for phase 2 can be up to 84 patients.

[REDACTED]

[REDACTED]

13.2 Analysis Sets

Safety analysis set: The safety analysis set will include all enrolled patients who receive at least 1 dose (even incomplete) of modakafusp alfa.

Response-evaluable analysis set: The response-evaluable analysis set is a subset of the safety analysis set including patients with measurable disease at baseline and at least 1 post-treatment response assessment.

PK analysis set: The PK analysis set will include those patients from the safety analysis set who have sufficient data to calculate at least 1 PK parameter for modakafusp alfa.

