8.0 STUDY DRUG

8.1 Study Drug Administration

All protocol-specific criteria for administration of study drug must be met and documented before drug administration. Study drug will be administered only to eligible patients under the supervision of the investigator or identified subinvestigator(s).

The initial dose should be based on a patient's weight at screening and only adjusted if there is a $\geq 10\%$ change in body weight.

Investigational sites should refer to the pharmacy manual for preparation of each dose. Modakafusp alfa doses < 1.5 mg/kg will be administered over 1 hour (± 10 minutes). Modakafusp alfa doses ≥ 1.5 mg/kg will be administered over 2 hours (± 10 minutes) and could be extended to 4 hours at the investigator's discretion. Any decrease in infusion duration must be discussed with and agreed upon by the sponsor. If a patient presents with an infusion-related reaction at any dose level, the duration of the infusion may be extended per investigator's discretion. Total time from modakafusp alfa dosing solution preparation until end of infusion must not exceed 7 hours.

In the combination treatment cohorts, the recommended pembrolizumab dose of 400 mg will be administered as an IV infusion over 30 ± 10 minutes Q6W in combination with modakafusp alfa. Please see premedication and observation guidelines in Section 8.8.1.

Pembrolizumab will be administered before modakafusp alfa on days when both modakafusp alfa and pembrolizumab are given. At least 30 minutes should elapse between the completion of the infusion of the first study drug and the initiation of the infusion of the second study drug.

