7.3 Analysis Sets

- Safety Analysis Set: The safety analysis set will include all enrolled patients who received at least one dose (even incomplete) of the study drug.
- Response evaluable Analysis set: The response evaluable analysis set is a subset of the safety analysis set including patients with measurable disease at baseline and at least 1 post-treatment evaluation.
- DLT Evaluable Analysis Set: patients who receive all Cycle 1 doses of modakafusp alfa or experience a DLT in Cycle 1 in the dose-escalation portion of the study; or patients who receive all Cycle 1 doses of modakafusp alfa in combination with pembrolizumab or experience a DLT in Cycle 1 in the safety lead-in portion of the study.
- Pharmacokinetic Analysis Set: patients from the safety analysis set who have sufficient data to calculate at least 1 PK parameter for modakafusp alfa.
- Immunogenicity-evaluable Analysis Set: Includes patients with a baseline and at least one post-baseline immunogenicity assessment.

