7.8 Study Drug Exposure and Compliance

Extent of Exposure

The exposure to study drugs (modakafusp alfa and Pembrolizumab) will be characterized by summaries and descriptive statistics of duration of treatment in weeks, number of treated cycles (1, 2, 3, 4, 5, 6, 7-12, >12 and summary statistics), and relative dose intensity will be summarized by safety analysis set.

A treated cycle is defined as a cycle in which any amount of the study drug for at least one of the dosing days in the cycle is given.

Cumulative dose (mg/kg): sum of all doses of the study drug administered to a subject during the treatment period.

Relative dose intensity = (actual dose per week / planned dose per week) × 100. The actual dose per week adjusts for delays in the start of a cycle and assumes the last cycle is fixed at the intended duration.

- Date of last exposure of the study drug = min(date of last dose of the study drug + treatment interval - 1, date of death, start date of the subsequent treatment - 1). This algorithm may be adjusted as appropriate by consulting the study clinician.

Actual dose per week and planned dose per week are calculated as follows:

- Actual dose per week: cumulative dose of the study drug in mg/kg / [(date of the last exposure of the study drug – date of the first dose + 1) / 7].
- Planned dose per week: starting dose of study drug (mg/kg) on C1D1 / treatment interval in weeks.

Action on Study Drug

The reason for dose modification (increased, reduced, interrupted, withdrawn, delayed, drug infusion interrupted, infusion rate increased, infusion rate reduced) of the study drug will be summarized by cycle for the safety analysis set.

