7.12 Safety Analysis

7.12.1 Adverse Events

Adverse events will be coded using the Medical Dictionary for Regulatory Activities (MedDRA) Version 23.0 or later (based on version at time of database lock). Treatment-emergent is defined as any AE that occurs on or after the date of the first dose of any study treatment through 30 days after the last dose of any study treatment.

Treatment-emergent AEs will be summarized by MedDRA system organ class (SOC), and preferred term. For summary tabulations the following hematologic abnormalities coded to MedDRA preferred terms in the Investigations SOC will be pooled with the appropriate clinical terms in the blood and lymphatic system disorders SOC:

MedDRA Preferred Term (Investigation SOC)	Mapped to (Blood and lymphatic system disorders SOC)
Neutrophil count decreased	Neutropenia
Platelet count decreased	Thrombocytopenia
Hemoglobin decreased	Anemia
White blood cell count decreased	Leukopenia

Treatment-emergent AEs will also be summarized by the National Cancer Institute Common Terminology Criteria for Adverse Events (NCI CTCAE) version 5.0.

Summary tabulations will include the following categories:

- Treatment-emergent AEs.
- Drug-related treatment-emergent AEs.
- Grade 3 or higher treatment-emergent AEs.
- Grade 3 or higher drug-related treatment-emergent AEs.
- Grade 3 and Grade 4 TEAEs (based on maximum severity).
- Grade 3 and Grade 4 drug-related TEAEs (based on maximum severity).
- The most commonly reported treatment-emergent AEs (i.e., those events reported by $\geq 10\%$ of all patients in each phase or overall population as appropriate).
- Serious treatment-emergent AEs.
- Drug-related serious treatment-emergent AEs.
- Treatment-emergent AEs resulting in discontinuation of study drug.
- Treatment-emergent AEs resulting in study drug modifications (including discontinuation, delay, reduction, and interruption).

- Treatment-emergent AEs resulting in dose delays.
- Treatment-emergent AEs resulting in dose reductions.
- Treatment-emergent AEs resulting in dose interruptions.
- TEAEs leading to death
- Treatment emergent AESI – all grades
- Treatment emergent AESI grade 3 and above
- Treatment emergent AESI grade 3 or 4
- Treatment-emergent AEs resulting in infusion rate reductions.
- Treatment-emergent AEs resulting in infusion interruptions.
- Serious treatment emergent AESI

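### In phase 2 the protocol's safety set omits a patient given pembrolizumab but never modakafusp alfa, and the SAP's undefined term for study drug does not settle whether that patient counts

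*Protocol*

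**What the plan says.** Protocol section 13.2 admits to the safety analysis set "all enrolled patients who receive at least 1 dose (even incomplete) of modakafusp alfa". SAP section 7.3 admits "all enrolled patients who received at least one dose (even incomplete) of the study drug" and does not say which drug that is.

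On the order of dosing, protocol section 8.1 states: "Pembrolizumab will be administered before modakafusp alfa on days when both modakafusp alfa and pembrolizumab are given". It requires at least 30 minutes between "the completion of the infusion of the first study drug and the initiation of the infusion of the second study drug", so it treats both agents as study drugs.

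The SAP points both ways. Section 7.8 opens with "The exposure to study drugs (modakafusp alfa and Pembrolizumab) will be characterized", which covers both agents. The same section then defines planned weekly dose as "starting dose of study drug (mg/kg) on C1D1 / treatment interval in weeks", which suits weight-based modakafusp alfa but not a flat 400 mg dose of pembrolizumab. Section 7.12.1 defines a treatment-emergent event as "any AE that occurs on or after the date of the first dose of any study treatment", which includes a first dose of pembrolizumab.

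The TEAE summaries (protocol 13.10, SAP 7.12.1) and the PFS and OS analyses (protocol 13.4, SAP 7.9) all use the safety set.

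**The concern.** A safety population should contain everyone exposed to the regimen whose safety is being described. In phase 2 that regimen is the combination, and exposure starts with pembrolizumab. A rule tied to modakafusp alfa removes a patient whose treatment ends between the two infusions, or who for any other reason never goes on to modakafusp alfa. If an adverse reaction is the reason, whether the patient is in the set depends on the outcome that the set exists to measure.

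The event at issue is one the plan sets out to capture: protocol section 10.2.1.2 and SAP section 7.12.1 both name infusion-related reaction as an event of special interest for pembrolizumab. Under the protocol wording, such an event could qualify as treatment-emergent by the SAP's dating rule and still appear in no TEAE table, because the patient is not in the analysis set.

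**Working it through.** The plan states no figure on this point, so the check compares the texts and then sizes the effect.

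**Step 1. Who is in the set, for a phase 2 patient**

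| Received | Protocol 13.2 | SAP 7.3, if study drug means modakafusp alfa | SAP 7.3, if study drug means either agent |
|---|---|---|---|
| Both agents | in | in | in |
| Modakafusp alfa only | in | in | in |
| Pembrolizumab only | out | out | in |

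Only the third row matters. In phase 1b modakafusp alfa is the sole drug, so the definitions agree.

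**Step 2. Can the third row occur?** Pembrolizumab comes first, with a gap of at least 30 minutes (protocol 8.1). A Grade 3 or 4 reaction to pembrolizumab stops that infusion and ends pembrolizumab (protocol 8.10.1.2). This does not by itself rule out modakafusp alfa: sections 8.6.3.2 and 8.6.4 let it continue when pembrolizumab stops for reasons other than immune-related events. The patient is lost from the set only if modakafusp alfa is never given, on Cycle 1 Day 1 or later.

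**Step 3. Which outputs are affected?**

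- *Affected:* TEAEs, SAEs, and TEAEs leading to dose modification or discontinuation. These are primary endpoints in the lead-in and secondary in the expansion. PFS and OS are also affected, as are the disposition and demographic tables (SAP 7.4 and 7.5). The screen-failure table in SAP 7.4 covers patients who were not treated, so a pembrolizumab-only patient does not belong there either.
- *Not affected:* the DLT count. SAP 7.3 gives it a separate DLT-evaluable set, and protocol 8.2 excludes events clearly unrelated to modakafusp alfa.
- *Little affected:* the primary ORR. The response-evaluable set is a subset of the safety set but also needs a post-treatment response assessment, which a patient who leaves this early would usually lack.

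**Step 4. Effect of one such patient.** Suppose that this patient has the event and no other patient does. Including the patient gives 1/n; excluding the patient gives 0/(n − 1). Intervals are exact 95% (Clopper-Pearson).

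| Group | Included | Excluded |
|---|---|---|
| Lead-in, n = 3 | 1/3 = 33.3% (0.8 to 90.6) | 0/2 = 0% (0 to 84.2) |
| Lead-in, n = 6 | 1/6 = 16.7% (0.4 to 64.1) | 0/5 = 0% (0 to 52.2) |
| Lead-in, n = 9 | 1/9 = 11.1% (0.3 to 48.2) | 0/8 = 0% (0 to 36.9) |
| Cohort, n = 25 | 1/25 = 4.0% (0.1 to 20.4) | 0/24 = 0% (0 to 14.2) |

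**Step 5. How likely is at least one?** The documents give no rate of pembrolizumab-only patients. Let p be that rate, assumed to lie between 0.1% and 2%. The chance of at least one among n patients is 1 − (1 − p)^n. The phase 2 maximum is 3 × 25 + 9 = 84, as protocol 13.1.2 states.

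| Assumed p | n = 3 | n = 9 | n = 84 |
|---|---|---|---|
| 0.1% | 0.3% | 0.9% | 8.1% |
| 0.5% | 1.5% | 4.4% | 34.4% |
| 1% | 3.0% | 8.6% | 57.0% |
| 2% | 5.9% | 16.6% | 81.7% |

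**The case against.** The strongest reply is that a set keyed to the investigational agent is a legitimate choice. Protocol 13.10 speaks of the safety of modakafusp alfa, and section 8.13.2 calls pembrolizumab background therapy. Counting a patient never exposed to modakafusp alfa adds to the denominator of its event rates. The events are not lost to the trial either: adverse events are collected from consent (protocol 10.3), and SAP 7.12.1 lists every death whether on study or not. PFS and OS are descriptive. This limits the harm to who appears in the summary tables. It does not remove the problem, because the regimen being described is the combination, and the SAP dates treatment-emergent events from "on or after the date of the first dose of any study treatment".

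A reader might also infer four stronger things that the documents do not support.

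- *Every patient stopped by a pembrolizumab reaction is dropped.* Sections 8.6.3.2 and 8.6.4 allow modakafusp alfa to continue in some of these patients, who then enter the set.
- *The protocol and SAP are shown to define different populations.* They may or may not. If study drug is read as modakafusp alfa, a reading that the mg/kg wording in SAP 7.8 and the heading and opening of protocol 8.6.4.1 both allow, the two sets coincide and both omit the patient.
- *A combination effect is hidden.* A reaction before any modakafusp alfa is toxicity of the assigned regimen, not evidence of an interaction.
- *All primary safety endpoints are affected.* The DLT count is not.

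**Conclusion.** The point holds for phase 2 only, and for one kind of patient: given pembrolizumab, never given modakafusp alfa. The protocol's safety set excludes that patient. The SAP's set includes or excludes the patient according to the meaning of an undefined term. The SAP cannot be assumed to settle the matter: version 3 follows Amendment 4, the current protocol is Amendment 6, and the SAP's summary of changes does not mention the safety set.

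The case is rare, and its frequency here rests wholly on an assumed range. At 0.1% to 2%, at least one such patient among 84 has a chance of about 8% to 82%. In the lead-in the chance is much smaller (0.3% to 5.9% with 3 patients, 0.9% to 16.6% with 9), but that is where one patient weighs most. The percentages for a single patient are conditional on the case occurring; they are not an expected bias. No trial conclusion is overturned, but the populations should be aligned before database lock.

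**What to change.** Put one definition in protocol section 13.2 and SAP section 7.3: every enrolled patient who is given any amount, including a partial infusion, of modakafusp alfa or pembrolizumab. State in both documents that the date of that first dose of either agent is time zero for TEAEs, PFS and OS, so that the population and the clock rest on the same event.

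The cost is a sentence or so in each document. It changes no dosing or clinical rule, leaves phase 1b as it is, and matches the SAP's existing TEAE definition. The downside is that a pembrolizumab-only patient would appear in the tables and count in the denominators without exposure to modakafusp alfa. A footnote giving the number of such patients deals with that.
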